#### 9.4. Data sources

In Indonesia Vaccine Safety Website for AEs reported following administration of BNT162b2 mRNA vaccine

#### 9.5. Study size

This is a descriptive study without a statistical hypothesis and hence sample size calculation is not applicable. In this study all the AEs reported following administration of BNT162b2 mRNA vaccine

will be collected retrospectively from the onset of this vaccine administration in Indonesia till the time of approval of this study.

#### **9.6. Data management**

Data will be obtained from the Indonesia Vaccine Safety Website for AEs reported following administration of BNT162b2 mRNA vaccine as per the variables listed in section 9.3. A data management plan will be created before data collection begins and will describe all functions, processes, and specifications for data collection and analysis.

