**B4. Solicited AEs:**

PFIZER CONFIDENTIAL

B4.1.. Local reactions : pain, swelling, redness, thickness.

B4.2. Systemic reactions: fever, myalgia, malaise

B5. Unsolicited AEs:

B5.1. Local reactions: abscess, bleeding, etc.

B5.2. Systemic reactions: headache, nausea, arthralgia, etc.

Events for which either of the above is missing will not be recorded for analysis.

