### **9.2.1. Inclusion criteria**

This study will include adverse events reported in Indonesia NC AEFI database for individuals 12 years of age and older

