### **9.2.2. Exclusion criteria**

The incomplete data in the database will be excluded

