#### **9.7. Data analysis**

Descriptive Summary statistics will be presented to describe characteristics of events reports. Categorical covariates such as gender will be described by frequency distributions while continuous covariates such as age expressed will be summarized by in terms of their means and standard deviations or medians and interquartile ranges (IQR) as appropriate.

In addition, incidence rates will be computed as the number of events divided by the total number of vaccines administered.

All analyses will be done by Microsoft Excel

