## **11. MANAGEMENT AND REPORTING OF ADVERSE EVENTS/ADVERSE REACTIONS**

This study involves data that exist as structured data by the time of study start. In these data sources, individual patient data are not retrieved or validated, and it is not possible to link (ie, identify a potential association between) a particular product and medical event for any individual. Thus, the

PFIZER CONFIDENTIAL

minimum criteria for reporting an AE (ie, identifiable patient, identifiable reporter, a suspect product, and event) cannot be met.

[figure not shown]

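### Do the primary counts become ambiguous because age and gender are missing from the section 9.3 variable list?

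*Combined protocol and SAP*

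**What the plan says.** Five parts of the protocol bear on this point.

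- **Extraction.** Section 9.6 says data are obtained "as per the variables listed in section 9.3". It also promises a data management plan, to be written before collection, covering the specifications for collection and analysis.
- **Eligibility.** Section 9.2.1 takes in "adverse events reported in Indonesia NC AEFI database for individuals 12 years of age and older".
- **Exclusion.** Section 9.2, after listing outcome elements A1 to B5.2, ends: "Events for which either of the above is missing will not be recorded for analysis". Section 9.2.2 adds: "The incomplete data in the database will be excluded".
- **Analysis.** Section 9.7 states: "Categorical covariates such as gender will be described by frequency distributions while continuous covariates such as age expressed will be summarized". It adds that "incidence rates will be computed as the number of events divided by the total number of vaccines administered".
- **Scope.** Section 9.5 describes a study with no hypothesis and no sample size calculation. It opens its account of what will be collected with "In this study all the AEs reported following administration of BNT162b2 mRNA vaccine".

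Section 11, in explaining why individual adverse event reporting does not apply, says: "In these data sources, individual patient data are not retrieved or validated".

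**The concern.** Age decides eligibility and is to be summarised, and gender is to be summarised. Neither is in the table that governs extraction or in the element lists of sections 9.1 and 9.2. Taken literally, the plan uses two fields that it never says it will obtain.

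The omission seems to spread to the exclusion rules. The closing sentence of section 9.2 refers back to a list without age or sex, so a report lacking only one of these passes it. Section 9.2.2 could remove the same report, because it does not say what makes a record incomplete. The incidence rate divides events by all vaccines administered, so each report removed lowers the numerator and leaves the denominator alone. If the two rules were alternatives, two analysts could report different values for A1 (serious events), A2 (total events) and the rates, each consistent with the protocol. The section 11 sentence seems to add to this by suggesting that report-level age is not available at all.

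**Working it through.** The protocol states no event count, missing-data rate or sample size, so there is no figure to reproduce. The check is a comparison of passages plus one line of algebra.

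**1. Is the omission real?** Yes.
- The section 9.3 rows are vaccination type, SAE onset, causality, type of AE, solicited type, solicited local, solicited systemic, unsolicited type, unsolicited local, unsolicited systemic and seriousness: 11 rows, 0 for age or gender.
- The elements in sections 9.1 and 9.2 are A1, A2, B1, B2, B3.1, B3.2, B4.1, B4.2, B5.1 and B5.2: 10 elements, 0 for age or gender.

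**2. Do sections 9.2 and 9.2.2 conflict?** No. Section 9.2 removes reports with a missing listed item; it does not promise to keep every other report. Section 9.2.2 is the formal exclusion criterion. Two exclusion rules apply jointly, so a report that passes one and fails the other is excluded. If section 9.2.2 is read narrowly, it restates section 9.2 and the two agree. The only open question is what *incomplete* covers.

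**3. Which reports does that word affect?** Let N be the reports that pass section 9.2, a the share lacking age, s the share lacking sex only, and V the vaccines administered.
- A report with no age cannot be shown to meet the 12-or-older criterion, so under a strict reading of section 9.2.1 it drops out whichever meaning *incomplete* has.
- Narrow reading of section 9.2.2: rate = N(1 − a)/V.
- Broad reading, in which missing sex also excludes: rate = N(1 − a − s)/V.
- Ratio of broad to narrow = (1 − a − s)/(1 − a) = 1 − s/(1 − a). With a = 0 this is 1 − s.

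The documents give neither a nor s. Purely as an assumption, take a = 0 and s from 1% to 20%:

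| s (assumed) | Kept per 1,000, narrow | Kept per 1,000, broad | Ratio |
|---|---|---|---|
| 0% | 1,000 | 1,000 | 1.00 |
| 1% | 1,000 | 990 | 0.99 |
| 5% | 1,000 | 950 | 0.95 |
| 10% | 1,000 | 900 | 0.90 |
| 20% | 1,000 | 800 | 0.80 |

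The table returns the assumed s and nothing more. It is not evidence that the counts are exposed.

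**4. Can the section 9.2 rule be applied mechanically anyway?** No. B1 and B2 concern serious events only, and B4 and B5 separate solicited from unsolicited reactions. A non-serious report of injection-site pain alone could not carry all ten elements. Whoever applies the rule must already read it as covering the fields relevant to that report. Treating sex as not needed for a count of events is the same kind of judgement, and it fits the section 9.5 aim of gathering all reports.

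**5. Does section 11 rule out report-level age?** No. Read that literally, its sentence would equally rule out onset and causality for each event, which section 9.3 requires. It explains why the minimum criteria for reporting a case are not met and says nothing particular to age.

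**6. Is either field shown to be absent from the extract?** No. Section 9.2 introduces its list as information that the data include, not as a closed set. Sections 9.2.1 and 9.7 make the intention to hold age and gender plain.

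**The case for a change.** The best opposing case rests on missing sex. Sex plays no part in eligibility, so whether such a report counts does depend on an undefined word, and the answer reaches both primary outcomes and the rates. Nothing in the text before us settles it: quality control is marked as not applicable in section 9.8, section 9.9 rules out data validation, section 9 now points to no separate analysis plan, and the content of the data management plan is not given. Clarification would cost two table rows and a few sentences.

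The facts in that case stand: the list is short by two fields and the term is undefined. Handling of unknown age is also unstated; an analyst might keep such reports because the authorisation in section 7 is itself for ages 12 and older. What does not follow is that the plan gives a wrong result. No rule has been shown to produce a misleading count, and no figure supports a material share of reports without sex. Extra table rows would also gain little for extraction: planned data collection ended on 28 March 2023, before version 2.0 was dated 26 April 2023.

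**Conclusion.** No change to the plan is called for. The omission of age and gender from section 9.3 is real, but it is missing detail that an analyst can supply from sections 9.2.1 and 9.7. The supposed conflict between sections 9.2 and 9.2.2 disappears once both are read as exclusion rules applied together. The remaining uncertainty is confined to reports lacking only sex. Its size is s/(1 − a) of the count, with both shares unknown and s possibly zero.

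This conclusion assumes that the extract holds age and sex, which the documents neither confirm nor contradict. It also assumes that the analyst does not discard an otherwise usable event for want of a field used only in a descriptive table, and that the report follows the ordinary practice of stating how many events were excluded and why. If s turned out to be large and such reports had been dropped without mention, the counts and rates would be understated by that share. That would be a matter for reading the final report.

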#### **9.7. Data analysis**

Descriptive Summary statistics will be presented to describe characteristics of events reports. Categorical covariates such as gender will be described by frequency distributions while continuous covariates such as age expressed will be summarized by in terms of their means and standard deviations or medians and interquartile ranges (IQR) as appropriate.

In addition, incidence rates will be computed as the number of events divided by the total number of vaccines administered.

All analyses will be done by Microsoft Excel

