## STUDY PROTOCOL

### Study information

Title	Safety Profile of BNT162b2 mRNA SARS-CoV-2 Vaccine in Indonesia: A National Passive Surveillance.
Protocol number	C4591050
Protocol version identifier	Version 2.0
Date	26 April 2023
Active substance	ATC code: J07BX03 Tozinameran - Nucleoside-modified messenger RNA (modRNA) encoding the viral spike glycoprotein (S) of SARS-CoV-2
Medicinal product	BNT162b2 mRNA Vaccine
Research question and objectives	
The objective of the study is to characterize descriptively the BNT162b2 vaccination experience among the Indonesian population, by analyzing structured data within Indonesia Vaccine Safety Database as requested by Indonesia Food and Drug Monitoring Agency (BPOM).
 
Specific data elements include:
 

A. Primary outcome measure :

A1. SAE (Serious Adverse Event) : SAE after primary dose and/or booster dose

A2. Total AE reported after primary dose and/or booster dose

B. Secondary outcome measure :

B1. SAE onset : <math>\leq</math>30 mins or <math>></math> 30 mins

PFIZER CONFIDENTIAL

A large rectangular area of the page is completely blacked out with a thick black marker, obscuring several lines of text.

	
B2. Causality of SAE : coincidence, ISRR (Immunization Stress Related Response), vaccine reaction, unclassifiable, or indeterminate
 
B3. Type of AE :
 
B3.1. Serious and Non-serious
 
B3.2. Solicited and unsolicited
 
B4. Solicited AEs:
 
B4.1.. Local reactions : pain, swelling, redness, thickness.
 
B4.2. Systemic reactions: fever, myalgia, malaise
 
B5. Unsolicited AEs:
 
B5.1. Local reactions: abscess, bleeding, etc.
 
B5.2. Systemic reactions: headache, nausea, arthralgia, etc.

Author	
PPD MD
 
Pfizer
 
PPD

[figure not shown]
This document contains confidential information belonging to Pfizer. Except as otherwise agreed to in writing, by accepting or reviewing this document, you agree to hold this information in confidence and not copy or disclose it to others (except where required by applicable law) or use it for unauthorized purposes. In the event of any actual or suspected breach of this obligation, Pfizer must be promptly notified.

PFIZER CONFIDENTIAL

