**A. Primary outcome measure :**

A1. SAE (Serious Adverse Event) : SAE after primary dose and/or booster dose

A2. Total AE reported after primary dose and/or booster dose

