**B. Secondary outcome measure :**

B1. SAE onset :  $\leq$ 30 mins or  $>$  30 mins

B2. Causality of SAE : coincidence, ISRR (Immunization Stress Related Response), vaccine reaction, unclassifiable, or indeterminate

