#### **9.9. Limitations of the research methods**

This is a retrospective, observational study for secondary data collection and analysis of structured data regarding AEs reported in Indonesia NC AEFI database, following administration of BNT162b2 mRNA vaccine. The data availability will be contingent on the data provision by Indonesia NC AEFI post study approval by BPOM (Indonesia National Regulatory Authority). Since the data will originate and be owned by the Indonesia NC AEFI database, data validation and external quality control measures will not be applicable as a part of this study.

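### Section 9.7 calls passively reported events per dose incidence rates, 9.9 omits under-reporting, and incomplete events are dropped although primary outcome A2 is the total reported

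*Combined protocol and SAP*

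**What the plan says.** **The rate.** Section 9.7 plans descriptive summaries of event reports and adds that "incidence rates will be computed as the number of events divided by the total number of vaccines administered". The title calls the study "A National Passive Surveillance". Sections 9.1, 9.2 and 9.4 take the data from adverse events reported to the national vaccine safety website; no vaccinated cohort is followed.

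**The limitations.** Section 9.9 names the retrospective observational design and the dependence on data being provided, and says that "data validation and external quality control measures will not be applicable as a part of this study". Neither it nor any other section supplied mentions under-reporting.

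**The totals.** Section 9.5 says that "all the AEs reported following administration of BNT162b2 mRNA vaccine" will be collected. Primary outcome A1 is serious adverse events and A2 is "Total AE reported after primary dose and/or booster dose".

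**The exclusions.** After listing outcomes A1 to B5, section 9.2 closes with "Events for which either of the above is missing will not be recorded for analysis". Section 9.2.2 adds "The incomplete data in the database will be excluded". Neither place defines incomplete, and no count of excluded events is planned.

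**The concern.** There are two separate faults.

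The first is the label. A passive system records an event only if someone reports it. The share reported is unknown, so reported events over doses measures risk and reporting behaviour together. Calling it an incidence rate tells the reader that it measures risk alone, and the limitations section does not correct that impression.

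The second is the exclusion rule, which acts on the primary outcomes themselves. A2 is meant to be a total of what was reported, yet events with missing items are removed before analysis. The primary counts then depend on how completely the report was filled in, as well as on what was reported.

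Section 7 says that the national regulator asked for this analysis. As written, it would receive a safety figure called incidence without its main caveat, and totals that are smaller than the totals they are said to be.

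**Working it through.** The documents give no event count, dose count, rate or missing-data figure, so there is no stated number to reproduce. The check is algebra plus a comparison of the rules.

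**1. What the 9.7 figure measures.** Let r be the share of events that are reported and e the share of reported events dropped as incomplete. Then:

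computed figure = true events per dose × r × (1 − e)

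This equals the true events per dose only if r = 1 and e = 0 (duplicate or wrongly coded reports aside). The passive design gives no basis for r = 1, and the exclusion rules make e greater than 0 whenever an incomplete event exists. With e = 0 the figure is a reporting rate. With e above 0 it is a reporting rate among complete events only.

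**2. Whether 9.9 covers this.** Lack of validation concerns the accuracy of reports that arrived. Under-reporting concerns events for which no report arrived. The first does not imply the second, so the caveat is absent.

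**3. Which fields each outcome needs.**
- A2 needs only that an eligible event was reported after this vaccine.
- A1 needs that, plus seriousness.
- Onset is needed only for B1, and causality only for B2. Both are defined for serious events only.

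**4. What the exclusion rule does on each reading.**
- *Natural reading:* an event is dropped if an item that applies to it is blank. A serious event with blank onset or causality is then lost from A1, from A2 and from the rate numerator, although step 3 shows that neither field is needed to count it.
- *Strictest reading:* every listed item is required. Non-serious events have no entry for serious-event onset or causality, so all of them would be excluded. Outcome B3.1, which separates serious from non-serious events, shows that this cannot be intended, but the wording does not rule it out.

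**5. Size of the exclusion.** Relative to what was reported, totals and rates are multiplied by 1 − e. The values of e are assumed:
- e = 0.05: 1 − 0.05 = 0.95
- e = 0.10: 1 − 0.10 = 0.90
- e = 0.30: 1 − 0.30 = 0.70

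The doses behind dropped events were still given and belong in the denominator. The fault lies in the numerator.

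**6. Timing.** Section 6 planned data collection to end on 28 March 2023. This version is dated 26 April 2023, 29 days later, and the final report is planned for 19 June 2023, a further 54 days.

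**The case against.** The best defence is that little turns on the label. Section 9.7 introduces the rate as an addition and no listed outcome is a rate. The formula is stated openly, so a careful reader can see what was computed. Section 9.5 states that there is no hypothesis, 9.1 says that the study will make no recommendations on vaccine use, and no comparison with trial rates is planned. This limits the harm to a mislabelled figure without its main caveat. It does not make the label right, and in a descriptive study the numbers and their labels are the product.

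On the exclusion, the wording in 9.2 is ambiguous and the loss could be negligible. The causality options end with "vaccine reaction, unclassifiable, or indeterminate", so a doubtful case may carry a code instead of a blank. That helps only where the code was actually entered, and it does nothing for a blank onset. The ambiguity is a reason to define the rule.

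Some stronger inferences are tempting, and the documents do not support them:
- *That 9.5 contradicts the exclusions.* Section 9.5 says that all reported events are collected, and 9.2 says that some are not analysed. Collecting and then excluding is consistent. The conflict is with A2, which is worded as a total.
- *That the figure understates risk by a particular multiple.* Any multiple needs a value of r, and none is given. Under-reporting and exclusion lower the figure, while duplicate or coincidental reports could raise it.
- *That the share lost can be modelled from the number of listed items.* The documents do not show which items are separate database fields or how often each is blank.
- *That the dose denominator is undefined.* The protocol names no source or calendar cut-off for it, but the data management plan required by 9.6 is not among the documents and may state both. At most, a pointer is needed.

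**Conclusion.** The point holds in two parts and should be fixed before the final report. First, the 9.7 quantity is a reporting rate, and 9.9 lacks the caveat that would let a reader interpret it. This follows from the protocol's own description of the design and needs no assumption. Second, the exclusions in 9.2 and 9.2.2 make A2 and the rate numerator, and on the natural reading A1, smaller than the reported totals whenever an incomplete event exists. That part rests on how the ambiguous sentence in 9.2 is read; the conflict with A2 remains on either reading.

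The size is unknown. The 0.95 to 0.70 range illustrates an assumed 5% to 30% loss and is not an estimate, and no figure is claimed for under-reporting. The study contains no test or comparison that this would invalidate.

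**What to change.** - **9.7:** replace the incidence label with *reporting rates (reported events per 100,000 BNT162b2 doses administered)*, with events and doses covering the same age group (12 years and older) and the same period. Point to the data management plan for the dose-count source and cut-off date if it states them.
- **9.2 and 9.2.2:** count every reported event in persons aged 12 or older in A2, and every such event recorded as serious in A1, even if other fields are blank. Show missing seriousness, onset, causality or type as unknown in the breakdowns. State the number of incomplete events.
- **9.9:** state that, because of under-reporting and lack of validation, the rates are not incidences.

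**Cost.** The relabelling and the added limitation need no new data; matching doses to events needs an aggregate dose count for that age group and period. The reported figure will support a weaker conclusion. If incomplete events were left out of the extraction planned to end on 28 March 2023, they would have to be requested again before the report of 19 June 2023.

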#### **9.8. Quality control**

Not applicable

#### **9.9. Limitations of the research methods**

This is a retrospective, observational study for secondary data collection and analysis of structured data regarding AEs reported in Indonesia NC AEFI database, following administration of BNT162b2 mRNA vaccine. The data availability will be contingent on the data provision by Indonesia NC AEFI post study approval by BPOM (Indonesia National Regulatory Authority). Since the data will originate and be owned by the Indonesia NC AEFI database, data validation and external quality control measures will not be applicable as a part of this study.

#### **9.10. Other aspects**

Not applicable

PFIZER CONFIDENTIAL

## **10. PROTECTION OF HUMAN SUBJECTS**

### **10.1. Patient information**

This study involves data that exist in anonymized structured format and contain no patient personal information.

### **10.2. Patient consent**

As this study involves anonymized structured data, which according to applicable legal requirements do not contain data subject to privacy laws, obtaining informed consent from patients by Pfizer is not required.

